4.0 Changes from Previous Version of Approved SAP

This is the second version of the SAP. Changes from the first SAP version:

- Public disclosure tables have been added.
- Additional imputation rules for partial dates have been added for AEs.
- Sections of statistical analysis on PK and PD parameters have been changed slightly to allow for data driven model modifications. In addition, participants with parameter results for only one treatment will no longer be excluded from the statistical analyses.
- Descriptive statistics for routine urinalysis has been added.
- Headline summary PK TFLs as a separate deliverable and dry-run delivery have been removed.

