6.0 Study Design

This is a randomized, double-blind, single dose, 2-way cross-over study in healthy male and female participants with salbutamol. Salbutamol will be administered as a single 800 µg dose, given as 8 actuations at 20-second intervals, each delivering 100 µg as the ex-valve dose for a test treatment and a reference treatment. There will be a minimum washout period of 72 hours between treatment (dosing) periods.

Following a screening period of up to 28 days, eligible participants will be confined to the clinical research unit (CRU) from Day -1 until Day 5, (24 hours after the last dose on Day 4), when all study assessments are completed.

Thirty participants will be randomly assigned to one of 2 treatment sequences in 2 treatment interventions using a cross-over design:

Table 1: Treatment Sequences

Sequence
AB (n=15)
BA (n=15)

The following treatments will be administered as single 800 µg inhalation doses, given as 8 x 100 µg (ex-valve) at 20-second intervals:

- Treatment A: Salbutamol HFA-152a MDI (Test formulation).
- Treatment B: Salbutamol HFA-134a MDI (Reference formulation, currently approved Ventolin).

For the first dose of the treatment sequence, the first 2 participants will be randomized to one of the following: currently approved Ventolin, or Salbutamol HFA-152a MDI.

Remaining participants will be randomized only after review of at least 24 hours safety and tolerability data (i.e. adverse events (AEs) / serious AEs (SAEs), clinical laboratory values, vital signs and 12-lead ECGs)

from the sentinel participants by the Investigator or appropriately qualified delegate, in consultation with the Medical Monitor or delegate if unavailable, and it has been deemed safe to do so.

The remaining 28 participants will be dosed in various groups in accordance with CRO bed space and clinical resourcing CCI. The participant population will be assigned equally to the total number of treatment sequences.

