18.1.1 Adverse Events

All AE summaries will include only treatment emergent adverse events (TEAEs). TEAE are those which occur (or worsen) after the first dose of study drug.

TEAEs occurring following dosing in a specific period but before dosing in the next period will be attributed to that specific period. If the time is missing for an AE on a dosing day then the AE will be attributed to the treatment given on that day.

A summary overview of the number of events, and number and percentage of participants reporting TEAEs, TEAEs by severity, TEAEs by relationship, SAEs, and participants who discontinued study drug due to an AE will be provided.

A breakdown of the number of TEAEs, number and percentage of participants reporting each TEAE, categorized by body system and preferred term coded according to MedDRA (Version 25.0 or higher), will be presented by treatment and overall. One such table will be presented for all TEAEs and one such table will be presented for TEAEs considered to be related to the study medication.

Participants will only be counted once within each body system or preferred term.

The system organ class and preferred terms in these tables will be ordered by descending (total) number of participants per system organ class and within the system organ class per preferred term.

A summary of events reported, categorized by relationship not related vs related, will be provided by treatment and overall.

A summary of events reported, categorized by severity (categories as recorded in the eCRF: mild, moderate, severe) will be provided by treatment and overall. If AEs are judged as severe, the additional indication life-threatening or results in death will be combined in the summary, resulting in the following severities:

- mild
- moderate
- severe (no indication of life-threatening or fatal AE)
- life-threatening (severe AE with indication life-threatening)
- fatal (severe AE with indication results in death).

These tables will present the number of events, and number and percentage of participants per given category.

A listing of adverse events (AEs) leading to study discontinuation will be provided.

All AEs (including non-treatment-emergent events in a separate listing) recorded on the eCRF will be listed.

The following missing data will be imputed as defined (for calculations only / will not be presented):

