- Missing AE start and / or end times for the calculation of onset and duration will be assumed to be at 00:01 for a start time and 23:59 for end times
- Missing AE severity or relationship will be assumed to be severe or related, respectively
- Missing AE start times for the determination of treatment emergence will be assumed to occur after treatment unless partial date documents the AE as happening prior to treatment
- Missing AE start times for the determination of treatment assignment will be assumed to occur after treatment on the recorded date one minute after dosing
- Missing AE start date: First of the month will be used unless this is before the date of first study treatment of the cohort (i.e. clinic group); in this case the date of first study treatment date will be used.
- Missing AE end date: Last day of the month will be used, unless this is after the date of last visit of the cohort (i.e. clinic group); in this case the last visit date of the cohort will be used.
- Completely missing start or end dates will remain missing, with no imputation applied. Consequently, time to onset and duration of such events will be missing.

Onset of AEs related to treatment and duration of AEs will be calculated as follows:

Onset (time since last dosing in days, hours, minutes [dd hh:mm])	AE start date/time - treatment start date/time.
Duration (in dd hh:mm)	AE end date/time – AE start date/time.

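### The SAP's rule for AE start dates with a missing day nearly always places a Period 2 event before the Day 4 dose, which makes its onset wrong and leaves its product assignment unsafe

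*SAP*

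**What the plan says.** SAP section 4.0 records that this is new in the second version: "Additional imputation rules for partial dates have been added for AEs". In section 18.1.1 the start-date rule reads "Missing AE start date: First of the month will be used unless this is before the date of first study treatment of the cohort"; if it is before, "in this case the date of first study treatment date will be used". The cohort is explained there as the clinic group. The rule covers partial dates only (month known, day missing), because "Completely missing start or end dates will remain missing, with no imputation applied".

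The same section assigns events to products through periods: "TEAEs occurring following dosing in a specific period but before dosing in the next period will be attributed to that specific period". An event on a dosing day with no time has its own rule: "then the AE will be attributed to the treatment given on that day". A further bullet covers missing clock times: "Missing AE start times for the determination of treatment assignment will be assumed to occur after treatment on the recorded date". It relies on a known date.

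Onset is defined in 18.1.1 as AE start minus treatment start, and is labelled as the time since the most recent dose. SAP 9.1.2 describes the imputation of missing AE dates and times as serving onset and duration.

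On the schedule, SAP 6.0 has participants "confined to the clinical research unit (CRU) from Day -1 until Day 5, (24 hours after the last dose on Day 4"). Doses are on Day 1 and Day 4. The schedule of activities shows AE review on each of Days 1 to 5.

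**The concern.** The rule pulls an uncertain start date back towards the first dose. In a crossover whose two doses are three days apart in one stay, that first dose belongs to one product only. An event that followed the Day 4 dose will usually be dated to Period 1, and nothing in the rule refers to the Day 4 dose.

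Two outputs could suffer. Onset and duration are computed directly from the imputed start. The by-product AE tables suffer too if the imputed date is what the attribution rule reads. In sequence BA an event after HFA-152a would then be counted under the marketed inhaler, and in sequence AB the reverse. AE incidence by product is a secondary safety endpoint, and the protocol synopsis describes this as the first administration of salbutamol with HFA-152a.

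**Working it through.** The plan states no figure on this point, so there is none to reproduce.

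**Inputs.** Doses on Day 1 and Day 4, discharge on Day 5 (SAP 6.0). AEs are collected from the first dose to discharge, so a Period 2 event starts on Day 4 or Day 5. The imputation and attribution rules are those of SAP 18.1.1. Assumption: the clinic group's first-treatment date equals the participant's Day 1.

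**Rule as a formula.** Imputed start = the later of (first of the recorded month, Day 1). The event stays in Period 2 only if the imputed start is on or after Day 4; an imputed date equal to Day 4 goes to that day's treatment under the dosing-day rule.

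**Three example records for a Day 4 onset, with only May recorded.**
- Day 1 = 10 May, true start 13 May. Imputed 10 May (Day 1): before the Day 4 dose.
- Day 1 = 29 April, true start 2 May. Imputed 1 May (Day 3): before the Day 4 dose.
- Day 1 = 28 April, true start 1 May. Imputed 1 May (Day 4): stays in Period 2.

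**All Day 1 dates in 2023.**
- A Day 4 onset stays in Period 2 only when Day 4 is the 1st of a month: 12/365 = 3.3%. It moves for 353/365 = 96.7%.
- A Day 5 onset stays when Day 4 or Day 5 is the 1st: 24/365 = 6.6%. It moves for 341/365 = 93.4%.
- A Period 1 onset on Days 1 to 3 stays in Period 1 for 100% of dates, so the shift runs one way.

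The percentages are the same over 2022 to 2025. They are shares of calendar dates, not of observed events.

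**Effect on onset and duration.** When Days 1 to 5 fall in one month, the start date becomes Day 1. It is 3 days too early for a Day 4 onset (4 − 1) and 4 days too early for a Day 5 onset (5 − 1). Duration is lengthened by the same number of calendar days when the end date is known.

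**Effect on the product contrast, if the imputed date drives attribution.** Let w be the share of affected records that truly belong to Period 1, and f the fraction of Period 2 records that stay correctly assigned (0.033 to 0.066). Assume balanced sequences (15 AB, 15 BA) and the same product effect in each period. Period 1 records keep their full contrast; Period 2 records contribute f − (1 − f) = 2f − 1. The fraction of the true contrast retained is

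w + (1 − w)(2f − 1).

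- w = 0.5: 0.5 + 0.5 × (2 × 0.033 − 1) = 0.033, and with f = 0.066, 0.066. About 3–7% is retained.
- w = 0.75: 0.75 + 0.25 × (2 × 0.033 − 1) = 0.517, and with f = 0.066, 0.533. About 52–53% is retained.

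The documents do not give w. The value 0.75 is an assumption: records proportional to observation time, about 72 hours in Period 1 and 24 hours in Period 2.

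**Staggered dosing within a clinic group (conditional).** If the group's first dose is 1 to 3 days before the participant's own, a Period 2 event still leaves Period 2 for 93.4–96.7% of dates. For 84–87% of dates the imputed start is then before that participant's first dose. The documents do not say that dosing is staggered in this way.

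**The case against.** The strongest objection is that the SAP never says the imputed start date is used for treatment assignment. SAP 9.1.2 names only onset and duration, and the 18.1.1 bullets that mention treatment emergence or assignment concern missing times. This stands in part. A reader might infer that the SAP demonstrably credits 93–97% of partial-date Period 2 events to the wrong inhaler; the documents do not support that as a stated fact. On the narrowest reading, attribution of these events is undefined rather than wrong. That does not clear the rule. Section 9.1.2 is not exhaustive, since 18.1.1 also imputes times for emergence and assignment. The attribution rule has no other date to work from. And onset is wrong for a Period 2 event even on the narrow reading.

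A reader might also infer that the product difference in these records is almost erased. That needs an equal split of affected records between periods. Period 1 is observed for about three times as long, and at a 75% share roughly half the contrast survives.

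The use of the clinic group's date matters only if dosing is staggered. Even then, the emergence bullet presumes an event is post-treatment unless a partial date shows otherwise, so an early imputed date need not remove it from the TEAE tables.

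Finally, few records may be affected, perhaps none. Participants are confined, with AE review on Days 1 to 5. SAP 8.2 already routes questionable data to data management, and SAP 9.1.2 keeps partial dates as captured in the listings. All of this stands and limits the importance of the point.

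**Conclusion.** The point holds as a minor one. For 93–97% of possible calendar start dates, the rule dates a Period 2 event with a missing day before the Day 4 dose, so its onset is wrong. If the same date feeds period attribution, the event is tabulated under the Period 1 product. The SAP neither says that it does nor offers an alternative.

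The percentages assume that the clinic group's first-treatment date is the participant's Day 1. The dilution of the product contrast among these records ranges from almost complete (3–7% retained, equal split) to about half (52–53% retained, 75% in Period 1), given balanced sequences and a constant product effect. Because product labels are exchanged in both sequences, the error tends to blur a difference rather than favour one inhaler.

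The number of such records is unknown and should be small. For scale, with 30 participants exposed to each product, one participant moved is 1/30 = 3.3 percentage points of incidence. Safety is summarised descriptively, and the primary PK analysis is not touched.

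**What to change.** In SAP 18.1.1:

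- State that the first-of-month date is not used for treatment assignment.
- Assign an AE with a missing start day to the period in which it was first recorded at the daily AE review (Days 1 to 5), after a data query. For an event first recorded on Day 4, the query must establish whether it began before or after the dose.
- Flag any record that stays unresolved in the listing. Counting it under both products is possible, but it is a preference and would depart from the SAP's principle of one period per event.
- For onset and duration, use the later of the first of the month and the participant's own dose date in the assigned period. Set any missing clock time after that dose: the present 00:01 convention for onset would precede dosing, which protocol 8.11.1 places between 08:00 and 10:00.
- Replace the clinic group's first-treatment and last-visit dates with the participant's own.

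The cost is a few lines of SAP text and the matching programming of the AE analysis dataset before database lock.

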18.1.2 Deaths and Serious Adverse Events

A listing of deaths and other SAEs will be provided by participant.

If applicable, narratives of deaths, other SAEs, and other significant AEs will be described in the CSR.

18.1.3 Laboratory Data

Clinical laboratory data will be presented using units from the study data tabulation model (SDTM) Controlled Terminology.

All laboratory data will be listed, including laboratory variables not listed in the protocol. A separate listing, of out-of-normal-range values will also be provided. Normal ranges will be used directly from the clinical laboratory. An overview of clinical laboratory normal ranges is provided in separate document RefSet21001_21Jun21_4.pdf.

Clinical laboratory results outside the reference normal range will be flagged. In case the out of reference normal range values were considered clinically significant by the investigator, this will also be indicated in the listings. Comments with regard to the laboratory test results will be shown in a separate listing, and will cover reasons for not done measurements, specimen conditions, any comment available in the database related to laboratory measurements.

Descriptive statistics summarizing continuous laboratory results of clinical chemistry, hematology and routine urine analysis (observed values) by treatment and scheduled time will be provided.

Glucose

Linear plots of the arithmetic mean glucose concentrations by scheduled sampling time will be provided by treatment (2 treatments in one plot). These plots will show time in hours. The plots will match the summary table results.

Linear spaghetti plots of glucose concentrations by actual sampling times will be provided by treatment.

18.1.4 Vital Signs

Vital signs data (observed values) will be listed by participants and summarized descriptively by treatment per scheduled time point.

If SBP, DBP and/or pulse rate is out of the normal range, the physician's evaluation for that vital signs measurement will be listed. Normal ranges are as follows:

- SBP: 90 – 140 mmHg
- DBP: 50 – 90 mmHg
- Pulse Rate: 50 – 100 beats/min

If pulse rate is >85 beats/min at screening or day -1, the participant is not eligible for the study.

18.1.5 Electrocardiograms

The observed measurements for all ECG parameters (HR, PR, QRS, QT and QTc) and the corresponding abnormalities and physicians' conclusions will be listed by participant. The means of triplicate measurements for continuous parameters and the change from baseline of the mean triplicate measurements at each scheduled timepoint will be listed by participant.

Descriptive statistics will be provided to summarize mean ECG parameters (observed and changes from baseline) by treatment and scheduled time.

For heart rate and QTcF, linear plots of the arithmetic mean values (absolute values) by scheduled time will be provided by treatment (2 treatments in one plot). These plots will show time in hours. The plots will match the summary table results.

Linear spaghetti plots of the heart rate and QTcF values by actual times will be provided by treatment.

18.1.6 Other Observations Related to Safety

Bodyweight results will be listed.

19.0 Result Summary Public Disclosure Information

The following public study disclosure information will be provided:

- Summary of Subject Disposition at Each Study Period
- Summary Demographics
- Summary of Site Related Information
- Summary of Adverse Events Overview – Any AEs
- Summary of Adverse Events Overview – Any SAEs
- Summary of Adverse Events Overview – Any Drug Related SAEs
- Summary of Adverse Events Overview – Any Fatal SAEs
- Summary of Adverse Events Overview – Any Drug Related Fatal SAEs
- Summary of Common Non-serious AEs ($\geq 5\%$) by System Organ Class and Preferred Term
- Summary of All-cause Mortality - Occurrence of Death Due to Any Cause
- Summary of Urinary Dipstick Results

The complete list of result summary public disclosure tables will be provided in [Appendix 5: List of Public Disclosure Tables](#).

Appendix 1: Glossary of Abbreviations

Glossary of Abbreviations:	
ADAE	Adverse event analysis dataset
ADaM	Analysis data model
ADEG	ECG analysis dataset
ADLB	Laboratory analysis dataset
ADPC	Pharmacokinetic concentrations analysis dataset
ADPP	Pharmacokinetic parameters analysis dataset
ADSL	Subject-level analysis dataset
ADVS	Vital signs analysis dataset
AE	Adverse event
β-HCG	Beta-human chorionic gonadotropin
BMI	Body mass index
BQL	Below the quantifiable limit
CDISC	Clinical data interchange standard consortium
CI	Confidence interval
CRU	Clinical research unit
CSP	Clinical study protocol
CSR	Clinical study report
CV%	Coefficient of variation
CVw	Within participant coefficient of variation
DBP	Diastolic blood pressure
ECG	Electrocardiogram
eCRF	Electronic case report form
EDS	Early development services
FSH	Follicle stimulating hormone
geoCV%	CV% of the geometric mean
GSK	GlaxoSmithKline Research & Development Limited
ICH	The International Conference on Harmonization of Technical Requirements for Registration of Pharmaceuticals for Human Use
IRT	Interactive response technology
LLOQ	Lower Limit of Quantification
LSM	Least Square Means
Max	Maximum
MedDRA	Medical Dictionary for Regulatory Activities

MDI	Metered dose inhaler
Min	Minimum
PD	Pharmacodynamic
PK	Pharmacokinetic
RAMOS NG	Randomization and Medication Ordering System Next Generation
QA'd	Quality assured
QC'd	Quality controlled
SAP	Statistical analysis plan
SAE	Serious adverse event
SARS-CoV-2	Severe acute respiratory syndrome coronavirus 2
SBP	Systolic blood pressure
SD	Standard deviation
SDTM	Study data tabulation model
SmPC	Summary of product characteristics
TEAE	Treatment-emergent adverse event
TFL(s)	Tables, Figures and Listings
ULOQ	Upper Limit of Quantification
WHO	World Health Organization
WNL	WinNonlin
For PK and PD parameters please refer to Section 16 and 17	

Appendix 2: Schedule of Assessments

Procedure	Screening	Intervention period ^a						Discharge or early discontinuation	
	Study day	-28 to -1	-1	1 (pre-dose)	1	2	3	4	5
Confinement			X	X	X	X	X	X	X
Admission			X						
Discharge									X
Informed consent	X								
Inclusion and exclusion criteria	X	X	X						
Demography	X								
Physical examination ^b	X								X ^b
Body weight	X	X							
Height and BMI calculation	X								
Medical history (includes substance usage)	X								
Serum pregnancy test (females only)	X	X							X
FSH (females only)	X								
Serology (HBsAg, anti-HCV, anti-HIV 1 and 2)	X								
SARS-CoV-2 PCR test ^c		X				X			
Drug and alcohol screen	X	X							
Clinical laboratory assessments ^d	X	X							X
Blood sampling for serum potassium (PD) and glucose (safety) ^e				X ^e	X ^e			X ^e	
Vital signs ^f	X	X	X	X	X		X	X	X
12-lead ECG ^g	X	X	X	X	X		X	X	X
MDI teaching ^h		X	X				X		
Randomization			X						
Administration of study intervention ⁱ					X		X		
Blood sampling for PK ^j			X	X	X		X		X
AE review ^k				X ⁱ	X	X	X		X
SAE review ^k	X	X	X	X	X	X	X		X
Concomitant medication review	X	X	X	X	X	X	X		X

AE=adverse event; HCV=hepatitis C virus; HIV=human immunodeficiency virus; BMI=body mass index; ECG=electrocardiogram; FSH=follicle stimulating hormone; HBsAg=hepatitis B surface antigen; HR=heart rate; IMP=investigational medicinal product; MDI=metered dose inhaler; PCR= polymerase chain reaction; PD=pharmacodynamic(s); PK=pharmacokinetic(s); QTcF=QT interval corrected using Fridericia's formula; SARS-CoV-2= severe acute respiratory syndrome-corona virus type 2; SAE=serious adverse event;

- a. Participants will be in the clinic for 1 period, from Day -1 until Day 5 (24 hours after the last dose on Day 4).
- b. Complete physical examinations will be conducted at screening. Symptom driven physical examinations may be conducted at discharge or any other time, per the investigator's discretion.
- c. Sampling of nasal and throat mucosal cells for PCR testing for SARS-CoV-2. If deemed necessary, additional tests may be conducted during the study per site specific requirements.
- d. Clinical laboratory assessments (including clinical chemistry [includes liver chemistries], hematology, and urinalysis): at screening, on Day -1 (admission), and at discharge;
- e. Blood sampling for serum potassium (PD) and glucose (safety): on each dosing day (Day 1 and 4), blood samples will be taken pre-dose and at the following time points post-dose: 15 and 30 minutes and 1, 1.5, 2 and 4 hours post-dose.
- f. Vital signs (systolic and diastolic blood pressure, and pulse rate): vital signs will be recorded at screening, admission, on each dosing day (Day 1 and 4) at pre-dose and at the following time points post-dose: 15 and 30 minutes and 1, 1.5, 2 and 4 hours post-dose, and at discharge.
- g. 12-lead ECG: 12-lead ECG will be recorded at screening, admission, on each dosing day (Day 1 and 4) at pre-dose and at the following time points post-dose: 15 and 30 minutes and 1, 1.5, 2 and 4 hours post-dose, and at discharge. As the ECG parameters QTc and HR will be PD parameters, ECG will be measured in triplicate at pre-dose on Days 1 and 4. The 3 pre-dose measures will be averaged for QTc interval and HR to derive one baseline value. Each individual capture of the triplicate 12-lead ECG set will be separated by 1 to 5 minutes between the first and the third ECG. Post-dose 12-lead ECG measurements will be single measurements on both dosing days. Note: if an ECG meets potential stopping criteria, then the ECG measurement should be repeated in triplicate, with the averaged QT and QTcF used to determine stopping.
- h. Participants will be trained by using the CCI device on Day -1 and prior to each dosing on Days 1 and 4. Additional training instructions are provided using the CCI device which provides auditory feedback when the participant generates an adequate breath in:
Day -1: using the CCI device, review the instructions, with particular focus on Steps 4-7. Once the participant is comfortable with using the training device, practice completing a sequence of 8 puffs.
Dosing days: using the CCI device, review the instructions, and observe the patient performing a single puff using the training device. Provide feedback as necessary until proper technique is observed before conducting the full dose using the investigational inhaler.
Additional training using the CCI (eg, on Day 3) may be performed at the discretion of the clinic.
- i. Administration of study intervention: start of the 8 inhalations study intervention, with the inhalations administered at 20-second intervals. Note: All post-dose time points will be from start of dosing (first inhalation).
- j. PK blood sampling: on each dosing day (Day 1 and 4), PK blood samples will be taken at pre-dose, at 3, 5, 10, 15, 20, 30, and 45 minutes post-dose; and at 1, 1.5, 2, 3, 4, 5, 6, 8, 10, 12, 16 and 24 hours post-dose for plasma salbutamol determination. PK collection will be from start of study intervention (i.e. first inhalation). When assessments are scheduled at the same time, ECG and vital signs will be taken first followed by the blood samples, with PK blood sampling on time.
- k. All SAEs will be collected from the signing of the ICF until discharge.
All AEs will be collected from the start of study intervention until discharge.

